4.0 STUDY OBJECTIVES AND ENDPOINTS

The primary objective of the study is to evaluate the safety and effectiveness of the NEUWAVE™ FLEX MC Microwave Ablation System and Accessories used in transbronchial ablation procedures for adult subjects with oligometastatic tumors ($\leq 2\text{cm}$) in the lung.

In this study, “target” tumors are defined as lung tumors that are treated with FLEX MC at the index ablation procedure (i.e., Visit 2). A subject may have a maximum of two target tumors. “Non-target” tumors are defined as lung tumors that are treated with FLEX MC during study follow-up after completion of the primary endpoint, Technique Efficacy assessments at Visit 3 (i.e., Visits 3-6). A subject may not have more than three total tumors treated with FLEX MC (including target and non-target tumors).

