4.2 Safety Endpoint

- Adverse events (AEs) will be assessed from the time of subject consent.
 - Perioperative AEs will be captured from the time of subject consent through 30-days post any ablation procedure (i.e., the original ablation as well as any re-ablation) regardless of relationship to the study device or procedure.
 - AEs that are deemed related to the study device or procedure will be captured 30-days post any ablation procedure (i.e., the original ablation as well as any re-ablation) through the end of the study or early discontinuation.
 - Serious adverse events (SAEs) will be captured from the time of subject consent through the end of the study or early discontinuation regardless of relationship to the study device or procedure.

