5.0 INVESTIGATIONAL PLAN

5.1 Overall Study Design and Plan – Description

This is a prospective, multicenter, single-arm study focused on robotically-assisted transbronchial microwave ablation for adult subjects with oligometastatic tumors in the lung.

Principal Investigators across approximately 15 sites (United States, Canada, Hong Kong, and China) will be licensed pulmonologists/interventional pulmonologists or thoracic surgeons who have completed at least 20 diagnostic cases using the MONARCH Platform including at least 5 cases using CBCT and completed the Sponsor-required FLEX MC training.

Prospective subjects will be informed about the nature of the research, given the ICF to read, and if the subject understands the content, will be asked to provide consent by signing the ICF. Individuals scheduled for microwave ablation of the lung will be enrolled after providing informed consent and meeting study entry criteria. Subjects will be followed for 12 months following the first ablation procedure for safety and effectiveness outcomes. Enrollment will continue until up to 145 subjects are enrolled and treated. The Sponsor may also stop or pause enrolling new subjects prior to reaching 145 subjects based on either safety events, regulatory feedback, or inability to enroll appropriate subjects.

Subjects with oligometastatic tumors(s) in the lung who meet all inclusion/exclusion criteria will have transbronchial microwave ablation performed using cone beam CT (computed tomography) scan for probe guidance and confirmation.

The study will end when all enrolled and treated subjects have completed the 12-month, post-ablation follow-up period or have withdrawn consent prior to completion.

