6.0 STUDY PROCEDURES

6.1 Procedure Description(s)

Adult subjects with at least one oligometastatic tumor ($\leq 2\text{cm}$) in the lung located in the outer two-thirds and not closer than 1cm to the pleura (including fissures) with colorectal, renal, or sarcoma histology will have transbronchial microwave ablation performed using the MONARCH Platform.

Multidisciplinary Team

With regard to the clinical treatment approach for each patient, this is best assessed and determined by a local (i.e., site) multidisciplinary team (MDT) (aka tumor board) directly caring for the subject. An MDT discussion will be required prior to subject ablation to determine or ensure 1) that all oligometastatic tumors present at Screening are deemed treatable, 2) the manner/timing that all disease sites will be treated, and 3) the appropriateness of subject inclusion in the study. The MDT will include, at a minimum, a medical oncologist, thoracic surgeon or appropriate surgical specialist, and radiation oncologist.

Screening and Planning

A CT scan of the lung is used at Screening to determine tumor details (e.g., size, location, and type, if available). Tumor size must be measured in 3 axes (axial, sagittal, and coronal).

A maximum of two ipsilateral tumors that meet all inclusion and exclusion criteria may be ablated during a single session as part of this protocol. The second tumor may only be ablated if its planned ablation zone does not overlap with the ablation zone of the previously ablated tumor.

If a subject had three oligometastatic tumors that met all inclusion and exclusion criteria, but only two could be treated, per protocol, on the "Ablation Visit", the third, non-target tumor may be ablated at a later study visit. Similarly, if a new, non-target oligometastatic tumor is identified during study follow-up that meets all inclusion and exclusion criteria, it may be ablated. However, only up to three total oligometastatic lung tumors ("target" or "non-target") may be ablated as part of this protocol during the 12-month follow-up period.

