If target tumors recur after the original ablation, they may be re-ablated after the Visit 3 assessment for Technique Efficacy has been completed. A re-ablation will not change or extend the follow-up schedule. Additionally, no single tumor should be ablated more than twice during the 12-month follow-up period (i.e., the original ablation procedure and a re-ablation procedure at a separate visit). **Robotic Navigation Portion of Procedure**

Cone beam CT will be used in all cases to confirm the presence of the tumor(s) immediately before initiating the procedure. Navigation to the target tumor(s) will be performed using the MONARCH Platform. The MONARCH Platform is a novel robotic-assisted, software driven, endoscope articulation system which can electromechanically insert, steer, and withdraw a flexible endoscope to patient airways under continuous, real-time, direct, visual control by a physician operator.

Users must follow all instructions for use supplied with the MONARCH Platform, its components, instruments, and accessories, including any instructions for use (IFUs) provided with instruments or accessories. The provided IFU is the primary source for detailed safety information. The MONARCH Platform and its accessories are intended to provide bronchoscopic visualization of and access to patient airways for diagnostic and therapeutic procedures.

Microwave Ablation Portion of Procedure

The ablation will be performed using the NEUWAVE FLEX MC Microwave Ablation System, per the device's User Manual and Instructions for Use (IFU), and the performing physician's clinical judgment.

All ablations will be performed under general anesthesia via a transbronchial approach. Prophylactic antibiotics should be administered pre-ablation per site SOC.

The size of the tumor(s) will be measured and recorded on the day of ablation (Visit 2). Afterwards, the Monarch Platform will be used to navigate the microwave ablation probe to the target tumor and CBCT will be used to confirm probe position/placement.

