7.6 Visit 6 – 12-month Follow-up

Visit 6 occurs 12 months (\pm 1 month) after the first ablation procedure. The subject will visit the study site for the following assessments:

- Document any changes or updates to the subject's relevant concomitant medications (blood thinning/anticoagulants, antiplatelets, opioids, systemic chemotherapy, systemic steroids, immunotherapies, anti-inflammatories, NSAIDs, antibiotics, and medications used to treat adverse events)
- Document any changes or updates to the subject's concomitant procedures.
- Complete two validated quality of life questionnaires: EORTC QLQ-C30 and the lung-specific QLQ-LC13. These questionnaires should be administered in person, during the study visit. However, they may be administered over the phone, when needed.
- Collect key vitals: blood pressure, heart rate, and pulse oximetry.
- Evaluate ECOG performance status.

- Obtain PFTs, which include Spirometry (e.g., FEV1, FVC, FEV1/FVC, FEF25-75, Peak Expiratory Flow, and Maximum Ventilation Volume), Diffusion Capacity (DLCO), Total Lung Capacity (TLC), Functional Residual Capacity (FRC), and Residual Volume (RV).
- Complete chest CT, abdomen and pelvis CT, brain MRI (if site SOC), and extremity CT or MRI (if site SOC) to determine Tumor Progression. Contrast-enhanced images are preferred but not required. If a site takes a PET scan per SOC, the other images should also be taken, per protocol:
 - Local Tumor Progression (LTP), defined as recurrence of the originally ablated tumor(s) within or abutting the ablation zone using Chest CT and the 30-day post-ablation imaging as the baseline.
 - Regional Tumor Progression includes new or progression of pre-existing tumors that were not previously ablated within either lung using chest CT.
 - Distant Tumor Progression includes new or progression of pre-existing tumors outside of the lung using abdomen and pelvis CT, brain MRI, and extremity CT or MRI.
- Record any applicable AEs or SAEs:
 - Record any AEs or SAEs that may have occurred within 30 days of an ablation or re-ablation procedure.
 - Record only device- or procedure-related AEs or any SAEs that may have occurred after 30 days of an ablation or re-ablation procedure.

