12.0 ASSESSMENT OF SAFETY

Subjects will be evaluated for AEs and SAEs from the time of consent based on the following descriptions:

- Perioperative AEs will be captured from the time of subject consent through 30-days post any ablation procedure (i.e., the original ablation as well as any re-ablation) regardless of relationship to the study device or procedure.
- AEs that are deemed related to the study device or procedure will be captured 30-days post any ablation procedure (i.e., the original ablation as well as any re-ablation) through the end of the study or early discontinuation.
- Serious adverse events (SAEs) will be captured from the time of subject consent through the end of the study or early discontinuation regardless of relationship to the study device or procedure.

Investigators should remind study subjects to notify and/or see them or their study team first, when possible, if they experience any adverse events versus seeking treatment elsewhere.

Ongoing Review

The Sponsor will also review complications periodically, as per the study's Safety Management Plan.

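### After a late repeat or non-target ablation, the 30-day adverse-event window can run past Visit 6, and no visit or call is timed to complete it

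*Protocol*

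**What the plan says.** - **Safety window.** Protocol Section 4.2 captures perioperative adverse events "through 30-days post any ablation procedure (i.e., the original ablation as well as any re-ablation) regardless of relationship" to device or procedure. Protocol Section 12.0 and SAP Section 8.11 repeat this.
- **Later ablations.** Protocol Section 6.1 lets a recurrent target tumor be re-ablated once the Visit 3 efficacy assessment is done. It also says that up to three lung tumors "may be ablated as part of this protocol during the 12-month follow-up period". Section 4.0 places treatment of non-target tumors in Visits 3 to 6. These rules limit how many tumors are ablated and how often. None sets a latest date before Visit 6.
- **Fixed schedule.** Section 6.1: "A re-ablation will not change or extend the follow-up schedule". Section 5.1, repeated in SAP Section 1: "Subjects will be followed for 12 months following the first ablation procedure for safety and effectiveness outcomes", and "The study will end when all enrolled and treated subjects have completed the 12-month, post-ablation follow-up period" or have withdrawn consent.
- **Last contact.** Visit 6 is at 12 months ±1 month. Its safety instruction (Section 7.6) looks back: "Record any AEs or SAEs that may have occurred within 30 days of an ablation or re-ablation procedure".
- **Partial cover.** Section 12.0: "Investigators should remind study subjects to notify and/or see them or their study team first, when possible, if they experience any adverse events". Section 7.7 says what to record if an unscheduled visit takes place. Section 12.2 follows events already reported until they resolve or stabilize.

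**The concern.** Each rule is reasonable alone, but together they leave a gap. The plan defines a 30-day window after every ablation and allows ablations late in follow-up. It then ends planned contact at a visit whose date depends only on the first ablation. The duty to capture events remains, but no planned contact is timed to meet it.

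What is at stake is finding events after an invasive procedure done under general anesthesia. Two things in the protocol show why a contact is worth having. Section 14.0 plans a telephone or clinic safety contact after a lead-in diagnostic bronchoscopy, where nothing is ablated. Section 3.0 reports that one of 10 subjects in the sponsor's pilot died two weeks after the procedure of a presumed pulmonary hemorrhage. That pilot used a different navigation system, and a death would probably become known anyway. It does show that an important event can occur well into a 30-day window.

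**Working it through.** The plan gives no figure for late ablations, so there is none to reproduce, and the sample size plays no part. The inputs are the 30-day window (Protocol Section 4.2), the visit windows (Table 1) and the rules above. The plan counts in months. I assume 1 month = 30 days, 6 months = day 182 and 12 months = day 365 after the first ablation. Visit 5 then falls on days 152 to 212 and Visit 6 on days 335 to 395.

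**1. Days without planned contact.** Let k be the days from the ablation to Visit 6. Uncovered days = max(0, 30 − k).

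| k | Uncovered days | Share of window |
|---|---|---|
| 0 | 30 | 100% |
| 7 | 23 | 77% |
| 14 | 16 | 53% |
| 21 | 9 | 30% |
| 29 | 1 | 3% |
| 30 or more | 0 | 0% |

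**2. What the Visit 6 window could do.** For an ablation on day a, Visit 6 covers the whole window if it is held on day a + 30 or later. It can be held no later than day 395, so this works when a ≤ 395 − 30 = 365. Any ablation done by day 365 and before Visit 6 could therefore be closed by an in-window Visit 6. For example, take an ablation on day 325. Visit 6 on day 335 gives k = 10 and leaves 20 days uncovered. Visit 6 on day 355 leaves none. Both dates comply with the protocol, and no rule prefers the second.

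**3. Calendar exposure.** The affected ablation dates are the 30 days up to and including Visit 6. As a share of the time from day 30 to Visit 6:
- Visit 6 on day 335: 30/306 = 9.8%
- Visit 6 on day 365: 30/336 = 8.9%
- Visit 6 on day 395: 30/366 = 8.2%

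These are shares of time, not of subjects.

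**4. How an ablation could fall there.** No scan is scheduled between Visit 5 and Visit 6. The gap is 365 − 182 = 183 days, with extremes 335 − 212 = 123 and 395 − 152 = 243. To be done at most 29 days before Visit 6, an ablation prompted by the Visit 5 scan would have to wait at least 183 − 29 = 154 days (123 − 29 = 94 to 243 − 29 = 214). The case therefore needs an unscheduled or standard-of-care scan, or a long delay.

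**5. Effect on the tables.** SAP Section 8.11 counts subjects with an event. A missed event changes a percentage only if that subject does not already have the same event recorded.

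**6. Enrollment hold.** A death or a hemorrhage of grade 2 or higher within 30 days of an ablation stops enrollment (Protocol Sections 1.0 and 12.2). Enrollment is planned for 2 years and follow-up for 1, so early subjects can reach month 12 while enrollment has about 2 − 1 = 1 year left.

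**The case against.** The strongest reply is that nothing is cut short. Section 6.1 says the visit schedule is not extended, and Sections 4.2 and 12.0 and SAP Section 8.11 still require capture through 30 days. The Visit 6 window can absorb most late ablations, and the Visit 6 checklist already asks about events after a re-ablation. Subjects are told to report events, unscheduled visits record them, and known events are followed. Further arrangements may stand in the Safety Management Plan (Section 12.0) or the Safety Monitoring Plan (Section 12.1), which were not available.

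Much of this stands, and it sets the size of the point. A reader might infer that the plan shortens the safety window. It does not: the obligation is intact, and what is missing is a planned means of meeting it. A reader might also take an ablation at Visit 6, with all 30 days uncovered, as an ordinary case. The documents do not support that either. The Visit 6 list contains no ablation, Table 1 places procedure details at Visit 2 only, the procedure needs general anesthesia, and the reference to Visits 3 to 6 can simply mean the follow-up period.

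The reply does not supply a contact. The Visit 6 window helps only if a site chooses to use it. Reporting by subjects is passive, an unscheduled visit is not required, and following known events does not find new ones.

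**Conclusion.** The point holds as a minor gap in ascertainment: neither Visit 6 nor any later contact is tied to a late ablation. For k below 30, the last 30 − k days of the window have no planned contact unless the site happens to hold Visit 6 late enough. The number of subjects is unknown and probably very small. What may be missed is mainly non-serious events after late repeat or non-target ablations. The primary endpoint and index-procedure safety are unaffected.

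A reader might infer that the enrollment hold is undermined. The documents support less than that. Serious events must be reported within 72 hours of awareness, and the safety board reviews all deaths. The remaining risk is a rare late report of a relevant event while enrollment is still open.

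This rests on three assumptions. Day counts are approximated as stated. The 30-day rule for any ablation is taken to include non-target ablations, although its parenthesis names only the original and repeat procedures. For non-target ablations the gap comes from Sections 4.0 and 5.1, because the no-extension sentence names re-ablation only. The conclusion concerns the protocol and SAP, not safety plans kept elsewhere.

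**What to change.** In Protocol Section 6.1, qualify "A re-ablation will not change or extend the follow-up schedule" with this clause, and repeat it as a Table 1 footnote:

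*except that AE/SAE capture continues through 30 days after the last study ablation (re-ablation or non-target): hold Visit 6 at least 30 days after that ablation where its window allows, otherwise make one phone contact at 30 days.*

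In Protocol Section 5.1 and SAP Section 1, extend both the follow-up sentence and the end-of-study sentence with *and through 30 days after the last study ablation, if later*.

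Two safeguards belong with it:
- **Censoring.** SAP Section 8.8.2 censors subjects without progression at the last contact date. A call could move that date up to 30 days beyond the Visit 6 scan. State that the call is for safety only and does not move the censoring date for PFS or LTPFS.
- **Completion status.** State that a missed call does not change a subject's Visit 6 completion status.

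The cost is one clause, one footnote, two aligned sentences in each document, a line on censoring and completion, and one call for a few subjects. Their safety close-out may move by up to 30 days. Barring ablation in the 30 days up to and including Visit 6 would need no call, but it would delay treatment or move it off study, so the timing rule with a fallback call is preferable.

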19. Subject who received systemic therapy (e.g., chemotherapy, targeted drug therapy, or immunotherapy) within 14 days prior to the planned study ablation procedure or those who plan to receive systemic therapy before completing the primary endpoint assessment (30 days post-ablation).
20. Uncontrolled hypertension pre-procedure (Visit 2). Defined as systolic blood pressure $\geq 160\text{mmHg}$ and/or diastolic blood pressure $\geq 100\text{mmHg}$ despite pharmacotherapy.
21. Subjects who have participated in an investigational drug or device research study within 30 days of enrollment that would interfere with the primary endpoint of this study.
22. Physical or psychological condition that would impair study participation.
23. Severe neuromuscular disease.
24. Subjects judged unsuitable for study participation by the Investigator for any other reason.

Intra-operative exclusion criteria that lead to stopping a procedure:

25. Inability to tolerate anesthesia.
26. Time of navigation to initiation of ablation longer than 60 minutes, per target tumor.
27. Bleeding estimated to exceed 50cc (visualization via the drainage system) or a Nashville grade 2 or higher intervention is required (see Appendix 2).
28. If the CBCT imaging after a bleeding episode obscures the radiographic visibility of the tumor such that the ablation probe/tumor relationship is not discernable, the procedure should be terminated.
29. Any presenting condition discovered intra-procedurally that in the opinion of the Investigator would make participating in this study not in the subject's best interest.

Note 1: For Exclusion Criterium 26, the procedure may be attempted again at a later time providing there were no other complications other than an extended navigation time.

Note 2: For Exclusion Criteria 27 and 28, the procedure may be attempted again at a later time, once, in the opinion of the physician, the area of bleeding is fully resolved.

Note 3: For any rescheduled ablations, the ablation should be rescheduled as soon as feasible

but no longer than four weeks after the originally scheduled ablation. Other than INR, other pre-ablation assessments do not need to be repeated.

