If the treating physician believes that bleeding during the navigation or ablation requires intervention, or if the bleeding obscures the view of the tumor or ablation zone, the physician is advised to terminate the procedure. The procedure may be attempted again at a later time, once, in the opinion of the physician, the area of bleeding is fully healed. The ablation should be rescheduled within four weeks of the originally scheduled ablation. Other than INR, other pre-ablation assessments do not need to be repeated.

If the target tumor(s) is within approximately 5mm of a major vessel (in the opinion of the treating physician), this tumor should not be ablated, or navigated to, for risk of puncture during the navigation. Additionally, tumors where the anticipated zone of ablation would encompass a significant (in the opinion of the treating physician) emphysematous disease and should also be avoided.

CBCT will be used to guide the microwave ablation probe to the target tumor(s) and ascertain the location of the probe after the robotic bronchoscope has been retracted. CBCT scans will be used at a minimum of three timepoints pre- and post- the ablation process:

- (1) Pre-Navigation: Prior to starting navigation, CBCT will be used to establish baseline imaging, confirm tumor details, and tumor segmentation for navigation (i.e., augmented fluoroscopy).
- (2) Pre-Ablation: Immediately before the ablation, use CBCT to confirm that the probe is in the intended location, and if it is not, reposition the probe.
- (3) Post-Ablation: After completing the ablation, use CBCT to confirm that the ablation margins are adequate.

The smallest and largest length of the entire ablation zone as well as the smallest ablation margin (i.e., distance from the edge of the ablation zone to the edge of the target tumor), must be measured in 3-dimensions and captured in the clinical database.

If a PET scan is taken during the follow-up period, the site must also perform the diagnostic CT as per protocol. PET scans, if obtained, should also be uploaded to the study imaging database with the other required images.

After the ablation procedure, the subject will be observed for up to 23 hours before discharge, except in cases where the Investigator deems it is necessary for the subject to remain hospitalized.

[figure not shown]
For specific details regarding the microwave ablation procedure and workflow between MONARCH and FLEX, please refer to the User Manual.

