11.0 RISKS AND BENEFITS OF THE STUDY

This study may or may not provide any benefits to the subject. However, the data collected throughout the study may help to assess the effectiveness and safety of a new ablation technique: robotic-assisted transbronchial microwave ablation of oligometastatic tumors in the lung.

Procedural Risks

The procedural risks associated with the FLEX MC transbronchial ablation procedure are expected to be similar to those associated with diagnostic bronchoscopy as well as those associated with thermal ablation, which in extremely rare instances could lead to death. The Sponsor plans on mitigating these risks during the clinical study by careful patient selection, implementing intraprocedural stopping rules, and the establishment of an independent DSMB to monitor the study.

Most commonly known risks for diagnostic bronchoscopy and thermal ablation procedures in the lung are summarized below by expected frequency: extremely rare (< 0.01%), rare (0.01% - 0.1%), uncommon (0.1% - 1%), common (1% - 10%), and very common (> 10%):

Known Risks for: Diagnostic Bronchoscopy	Known Risks for: Transbronchial Thermal Ablation Procedures in the Lung

RARE:
 
 Cardiovascular events 
UNCOMMON:
 
 Breathing difficulty Vocal cord spasm Vomiting Dizziness Bronchial spasm (muscle contraction of the airway) Hypoxemia (shortness of breath due to low levels of oxygen in the blood) 
COMMON:
 
 Pneumothorax (when air leaks into the space between the lungs and the chest wall) Hemorrhage (bleeding requiring medical intervention) 	
RARE:
 
 Bronchopleural fistula (abnormal passageway that develops between the large airways in the lungs and the space that lines the lungs) 
UNCOMMON:
 
 Air/Gas embolism (blockage or obstruction of a blood vessel) Infection 
COMMON:
 
 Pneumothorax (when air leaks into the space between the lungs and the chest wall) Hemorrhage (bleeding requiring medical intervention) Pleural effusion (buildup of fluid in tissues lining the lungs and the chest requiring tube drainage) Pneumonia 
VERY COMMON

	
 • Pain • Post-ablation syndrome
--	--

Anesthesia Risks

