16.2 Appendix 2: Nashville Scale for Bleeding

Grade	Findings at Bronchoscopy	Rationale
1	Suctioning of blood required for less than 1 minute	Minimal bleeding of no clinical consequence to the patient or the provider.
2	Suctioning more than 1 minute required or repeat wedging of the bronchoscope for persistent bleeding or instillation of cold saline, diluted vasoactive substances or thrombin	Requirement of one or more tools to control or prevent further bleeding.
3	Selective intubation with ETT or balloon/bronchial blocker for less than 20 minutes. Or premature interruption of the procedure.	Meaningful but short-term change in the clinical status of the patient involving more invasive procedures and causing interruption of the planned procedure.
4	Persistent selective intubation > 20 minutes or new admission to the ICU or PRBC transfusion or need for bronchial artery embolization or resuscitation.	Change in level of care and requiring advanced ventilatory support and/or transfusion of PRBC.

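### Protocol Section 5.4 sets a defined bleeding stop; Section 6.1 covers the same event with a physician-belief trigger and an advisory stop, and nothing says which governs

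*Protocol*

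**What the plan says.** Protocol Section 5.4 places criteria 25 to 29 under the line "Intra-operative exclusion criteria that lead to stopping a procedure". Criterion 27 is "Bleeding estimated to exceed 50cc (visualization via the drainage system) or a Nashville grade 2 or higher intervention is required". Criterion 28 deals with CBCT imaging after a bleed that "obscures the radiographic visibility of the tumor such that the ablation probe/tumor relationship is not discernable, the procedure should be terminated". Criterion 29 lets the investigator stop for any other condition found during the procedure. The Protocol Summary repeats these criteria. Note 2 to Section 5.4 allows another attempt after a stop under 27 or 28 once the physician considers the bleeding area resolved.

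Section 6.1, in the part on microwave ablation, treats the same situation in one sentence. It opens "If the treating physician believes that bleeding during the navigation or ablation requires intervention" and continues "or if the bleeding obscures the view of the tumor or ablation zone, the physician is advised to terminate the procedure". It gives no volume and no Nashville grade, and it does not point to criteria 27 or 28. It allows another attempt once the area has healed.

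Section 11.0 names "implementing intraprocedural stopping rules" as one of three ways of reducing procedural risk, with patient selection and the DSMB. No text says whether 5.4 or 6.1 takes precedence.

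**The concern.** A stopping rule reduces risk only if operators read it the same way. Here the trigger and its force both depend on which section is open. Section 5.4 gives an estimated volume or an intervention grade, and the procedure stops. Section 6.1 gives the operator's own view, and the stop is advice.

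The topic is not remote. Section 3.0 reports that bleeding was seen during prolonged navigation in one subject of the sponsor's 10-subject pilot. That subject died two weeks later of a presumed pulmonary hemorrhage, judged probably related to the procedure, and the sponsor stopped that study to revise its design.

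There is also an analysis consequence. Under Sections 5.2 and 5.6, a subject who is navigated but not ablated is either rescheduled or becomes an intra-operative screen failure outside the 145. Under SAP Section 6, a subject in whom microwave ablation is initiated belongs to the ITT set, on which the primary analysis is run. Whether a bleed during navigation stops the procedure can therefore decide who is analysed.

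**Working it through.** The point rests on text, so no arithmetic applies. The two rules side by side:

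| Element | Section 5.4 | Section 6.1 |
|---|---|---|
| Amount of bleeding | Estimated above 50cc (criterion 27) | None given |
| Intervention | Nashville grade 2 or above needed (criterion 27) | Physician believes intervention is needed; no grade |
| Imaging | Probe and tumor cannot be related on CBCT (criterion 28) | View of tumor or ablation zone obscured |
| Force | Leads to stopping (27); should be terminated (28) | Physician is advised to stop |
| Retry | Area resolved | Area healed |
| Time limit for rescheduling | Four weeks | Four weeks |

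Four example bleeds test whether the differences matter.

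1. *Above 50cc, operator judges that no intervention is needed, view clear.* The volume limb of criterion 27 is met, so 5.4 stops the procedure. Neither limb of 6.1 is met, so 6.1 read alone says nothing. The sections diverge.
2. *An intervention of Nashville grade 2 or above is needed and the physician recognises this.* Both sections are triggered, but 5.4 stops the procedure and 6.1 advises stopping. Only the force differs.
3. *Imaging obscured after a bleed.* Criterion 28 and 6.1 are close. Neither has a number. The remaining difference is again between a procedure that should be terminated and a physician who is advised to do so.
4. *50cc or less, Nashville grade 1 (suction for under a minute), but the physician believes intervention is needed.* Criterion 27 is not met and 6.1 advises a stop. Criterion 29 already admits a stop on the investigator's opinion, so the sections can be read together.

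The inconsistency that remains has three parts: example 1, the difference in force in examples 2 and 3, and the retry condition. If both sections are applied together, example 1 is still a stop, because criterion 27 is met whatever 6.1 says.

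**The case against.** The strongest reply is that Section 6.1 does not cancel Section 5.4. A site is bound by both, and Section 7.2 has the investigator review the eligibility criteria again on the day of ablation. Section 9.0 treats any activity outside the protocol's parameters as a deviation, so a monitor could class continuing after criterion 27 is met as one. This stands. A reader might infer that the same bleed will stop the procedure at one site and not at another, but the documents support only that it could.

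The contrast between a number and a judgement is also softer than it looks. The 50cc is an estimate, criterion 28 has no threshold, and criterion 29 is itself a judgement. A reader might infer that the sections clash in both directions; example 4 shows that they do not.

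A further inference concerns Appendix 2, where Nashville grade 3 includes "Or premature interruption of the procedure". It is tempting to say that a stop directed by the protocol raises the recorded severity of the bleed. The documents do not show this for any planned safety table. Section 12.1 grades adverse events by CTCAE, and Protocol Section 10.9 and SAP Section 8.11 specify hemorrhage of interest by CTCAE grade. The enrollment hold does mention Nashville grade, but it starts at grade 2, so moving from 2 to 3 changes nothing. For a grade 1 bleed, the hold text also speaks of severe hemorrhage needing more than local therapy.

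The reply does not remove the mismatch itself. The volume limb has no counterpart in 6.1, advice is weaker than a stop, and no precedence is stated.

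**Conclusion.** The inconsistency is real and should be corrected. It is confined to Section 5.4 criteria 27 and 28 with Note 2, repeated in part in the Protocol Summary, against one paragraph of Section 6.1. Its sharpest form is a bleed above an estimated 50cc that the operator judges to need no intervention and that leaves the view clear.

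The number of affected subjects cannot be computed. Section 11.0 classes hemorrhage requiring medical intervention as common, 1% to 10%, and a reader might multiply this by 145 to get 0.01 × 145 = 1.45 to 0.10 × 145 = 14.5 subjects. That would count the wrong group. It covers bleeds that do need intervention, where both sections are largely triggered, and it is not limited to bleeding during the procedure. The discordant bleeds have no rate in the documents, and subjects stopped before ablation who are not later ablated fall outside the 145. For the same reason, no size can be put on any effect on the primary analysis.

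The conclusion assumes that an operator may work from Section 6.1 without turning back to 5.4. The User Manual and Instructions for Use, to which 6.1 refers, were not available and might narrow the gap.

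**What to change.** The sponsor, with the DSMB, should reconcile the two sections and settle three things: one trigger for a bleeding stop, one status for it (mandatory or advisory), and one condition for a further attempt. The agreed rule should stand once, in Section 5.4 and the matching Protocol Summary entry. Section 6.1 should then refer to criteria 27 and 28 instead of restating them. Which rule is right is for the sponsor and DSMB to decide; no view is offered here.

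The cost is a wording change to the protocol and a short training note to sites. Sample size, endpoint definitions and the SAP are unaffected.
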